5.6.3 Partial Missing Treatment Failure Dates

For date of treatment failure, the following conventions will be used for imputing partial dates:

- If only the day of the month is missing, the 1st of the month will be used to replace the missing day. In cases where the date of death is present and complete, the imputed treatment failure date will be compared to the date of death. The minimum of the imputed treatment failure date and date of death will be considered as the date of treatment failure.
- If the day and month are missing or a date is completely missing, it will be considered as missing.

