2 INTRODUCTION

The purpose of this document is to provide details of the planned analyses for Study PIC10001. The primary analyses described in the main body of this document will be performed after all participants have completed the 2-year follow-up period in the study or discontinued early, and all corresponding data have been entered into the database, reviewed, and verified and the database locked. No changes to the SAP will be allowed at the time of or subsequent to database lock.

The analyses specified in this document supersede the high-level analysis plan described in the protocol.

Statistical analyses will be performed using SAS or R statistical software.

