5.4.2 Secondary Efficacy Endpoints

Disease Control Rate

DCR is defined as the proportion of participants who achieve SD, PR, or CR as measured by RECIST v1.1. That is, DCR is the number of participants whose BOR is SD, PR, or CR divided by the total number of participants in the population of interest. For SD, measurements must have met the SD criteria per RECIST v1.1 at least once after study entry, with disease assessment occurring at least 8 weeks after first study drug treatment.

DCR will be assessed at Week 12 (+7 days) and Week 18 (+7 days). DCR will be estimated within each treatment arm and 95% confidence intervals (CIs) will be estimated using the Clopper-Pearson method.

This study is not powered for statistical comparisons between arms. To aid in interpretation, each arm will be indirectly compared to the historical ipilimumab DCR of 28.5% (Hodi et al. 2010).

Time to Treatment Failure

TTF is defined as the time from first study drug treatment until the participant is started on another line of systemic therapy or participant death, whichever occurs first. Participants who are alive and do not start another therapy will be censored at the date of last follow-up. Time to event distributions will be estimated using Kaplan-Meier techniques.

Overall Survival

OS is defined as the time from first study drug treatment until death from any cause. Participants without documentation of death will be censored on the date of last contact. Time to event distributions will be estimated using Kaplan-Meier techniques.

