5.4.4 Sensitivity Analyses

No sensitivity analyses are planned for this study.

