5.6 Missing Data

5.6.1 Missing and Partial Missing Adverse Event Dates

Partially missing data of AE onset date may be imputed in order to avoid eliminating information from summary tables of TEAEs. If the day of an AE onset date is missing but both the month and year are available, the AE will be flagged as treatment-emergent if the date is conservatively estimated to be within 100 days after the last dose of study drug administration. Any AE deemed related to study drug will also be considered a TEAE regardless of elapsed time since last study drug administration. There will be no attempt to impute missing or partially missing dates for the listing of AEs.

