5.6.2 Partial Missing Death Dates

For death dates, the following conventions will be used for imputing partial dates:

- If only the day of the month is missing, the 1st of the month will be used to replace the missing day. The imputed date will be compared to the last known date alive plus 1 day, and the maximum will be considered as the death date.
- If the month or the year is missing, the death date will be imputed as the last known date alive plus 1 day.
- If the date is completely missing but the reason for death is present, the death date will be imputed as the last known date alive plus 1 day.

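### SAP 5.6.3 leaves a known start of new therapy with no usable date or stated event status for TTF when the month is missing, and its first-of-month rule has no lower bound

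*SAP*

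**What the plan says.** SAP 5.4.2 runs TTF from first dose to the start of another line of systemic therapy or death, whichever is first, and estimates it by Kaplan-Meier. Its censoring rule reads: "Participants who are alive and do not start another therapy will be censored at the date of last follow-up".

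SAP 5.6.3 has two conventions for incomplete failure dates. If only the day is missing, the first of the month is used, with a ceiling where a complete death date exists: "The minimum of the imputed treatment failure date and date of death will be considered as the date of treatment failure". For anything less complete: "If the day and month are missing or a date is completely missing, it will be considered as missing".

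SAP 5.6.2, for deaths, also uses the first of the month when only the day is missing, but with a floor: "The imputed date will be compared to the last known date alive plus 1 day", and the later date is taken. For less complete dates: "If the month or the year is missing, the death date will be imputed as the last known date alive plus 1 day". A wholly missing death date is handled the same way if a reason for death is recorded.

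SAP 5.4.4 adds: "No sensitivity analyses are planned for this study". SAP Section 2 adds: "No changes to the SAP will be allowed at the time of or subsequent to database lock".

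**The concern.** A participant known to have started new therapy has had a TTF event. If the month is unknown, 5.6.3 supplies no date, and Kaplan-Meier cannot place an event without one. The participant does not meet the censoring definition either, because another therapy was started. The programmer must then choose among censoring, exclusion, or waiting for a later death. These choices give different curves, the SAP selects none of them, and the choice would be made with the data in hand.

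The day-missing rule has a different fault. It always yields a date, but the date can be impossible, because nothing compares it with the first dose or with a contact at which the participant was documented free of new therapy.

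**Working it through.** **1. The two rules side by side**

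| What is missing | Death, SAP 5.6.2 | New therapy, SAP 5.6.3 |
|---|---|---|
| Day only | First of month, floor at one day after last known alive | First of month, ceiling at a complete death date, no floor |
| Day and month | Imputed from last known alive; event kept | Date missing; event status not stated |
| Whole date | Imputed if a reason for death exists; event kept | Date missing; event status not stated |

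The comparison with death sits only in the day-missing convention of 5.6.3, so it does not reach the last two rows.

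**2. What the missing floor allows (invented dates)**

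- First dose 20 March, new therapy in March, day unknown. The rule gives 1 March, so TTF = 1 − 20 = −19 days.
- Documented free of new therapy on 25 April, started later in April. The rule gives 1 April. A floor like that of 5.6.2 gives 26 April, 25 days later.

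**3. Size of the undated-failure gap**

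The documents state no TTF figure to reproduce. Inputs from the documents: 12 participants per arm, 24 months of follow-up, contacts as in Protocol Table 3 (days 0, 21, 42, 63, 84 and 105, then about every 91 days), and a survival median of 10.1 months for ipilimumab in Protocol 4.2. Assumed: exponential times, next-therapy median 6 months, an alternative survival median of 18 months, and 5% or 20% of next-therapy failures undated.

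True 12-month failure-free = 2^(−12 × (1/6 + 1/m)), with m the survival median:

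- m = 10.1: 2^(−12 × 0.2657) = 2^(−3.188) = 11.0%
- m = 18: 2^(−12 × 0.2222) = 2^(−2.667) = 15.7% (15.8% in the simulation below)

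Probability of a next-therapy failure within 24 months = (1/6)/(1/6 + 1/m) × (1 − 2^(−24 × (1/6 + 1/m))):

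- m = 10.1: 0.627 × 0.988 = 0.620
- m = 18: 0.750 × 0.975 = 0.731

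Expected undated failures per arm of 12: at 5%, 12 × 0.05 × 0.620 = 0.37 and 12 × 0.05 × 0.731 = 0.44; at 20%, 1.49 and 1.75.

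Simulated 12-month failure-free (400,000 participants per scenario):

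| Handling of undated failures | m = 10.1 | m = 18 |
|---|---|---|
| True value | 11.0% | 15.8% |
| Censored at last contact before the start, 5% undated | 11.6% | 16.8% |
| Censored at last contact before the start, 20% undated | 13.8% | 20.1% |
| Excluded, 20% undated | 11.1% | 16.2% |
| Counted at death, else censored at last follow-up, 20% undated | 17.5% | 25.2% |

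Censoring therefore overstates by 0.6 and 1.0 point at 5%, and by 2.8 and 4.3 points at 20%. Exclusion is nearly neutral on average. Waiting for death overstates by 6.5 and 9.4 points at 20%.

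**4. A hand check in one arm (invented data)**

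Take failures at 2, 3, 4, 5, 6, 8, 10 and 14 months, with four participants event-free at 24 months. The 24-month estimate is 4/12 = 33.3% and the median is 8 months. With one failure undated:

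- dropped: 4/11 = 36.4%
- censored at 24 months: 5/12 = 41.7%
- kept as an event dated one month early: 4/12 = 33.3%, median 7 or 8 months depending on which failure it is

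**5. Size of the missing floor**

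With the true day uniform over a 30-day month, the first of the month is early by (0 + 1 + … + 29)/30 = 14.5 days on average. The chance that it falls before the last contact is 14.5/91 = 15.9% with 91-day contacts and (210/21 + 9)/30 = 63.3% with 21-day contacts. With 20% of next-therapy failures lacking only the day, the unbounded rule lowers 12-month failure-free by at most 0.2 point and the median by 0.06 to 0.07 month.

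**The case against.** The strongest reply is that this is a wording gap in a descriptive secondary endpoint, unlikely to be triggered. Protocol 13.3 regards case report forms as complete only once missing data are resolved, Protocol 13.7 provides data quality reports, and SAP Section 2 requires review and verification before lock. With 24 participants, a month of therapy start can usually be recovered. At 5% undated, the chance that an arm of 12 has no such case is (1 − 0.05 × 0.620)^12 = 69% or (1 − 0.05 × 0.731)^12 = 64%. All this stands and limits the size, although the SAP itself foresees wholly missing failure dates by writing a rule for them.

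Four stronger readings are tempting, and the documents do not support them:

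- *The SAP deletes or censors the event.* The sentence concerns the date. Event status is left unstated, and a later death still supplies a TTF event, though a late one.
- *One or two participants per arm will be affected.* That needs the assumed 20%. No document gives a rate.
- *The SAP imputes every other kind of date.* For adverse events, SAP 5.6.1 says only that dates "may be imputed in order to avoid eliminating information from summary tables of TEAEs", and its stated rule covers a missing day with month and year known. Only 5.6.2 gives a real contrast.
- *New therapy is not collected on long-term calls.* Protocol 12.3.2 directs two-year TTF follow-up, Table 3 collects medications into follow-up, and the case report form is not among the documents.

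**Conclusion.** The point holds in a limited form. SAP 5.6.3 leaves a known failure without a usable date or a stated event status when day and month, or the whole date, are missing; the gap is plainest for a participant alive at last contact. Its day-missing rule, followed as written, can give a negative TTF or a failure before a contact documented free of new therapy. Neither conclusion depends on the simulation.

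The size does. About 0.5 to 1 point (5% undated) or 3 to 4 points (20% undated) on 12-month failure-free rests on exponential times, a next-therapy median of 6 months, survival medians of 10.1 to 18 months, and one handling, censoring at the last contact before the start, that the SAP does not prescribe. Sampling error in an arm of 12 is far larger: the SAP's own exact interval for 2/12 is 2.1% to 48.4%. The response-rate analysis does not use this rule. It is worth correcting because the correction is almost free, no sensitivity analysis would reveal the choice made, and the SAP closes to change at lock.

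**What to change.** Before database lock, amend SAP 5.6.3 as follows:

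- State that a known start of new systemic therapy remains a TTF event however incomplete its date.
- If only the day is missing, use the later of the first of the month and the day after the last date documented free of new therapy (at the earliest, the day after first dose), and no later than death.
- If day and month, or the whole date, are missing, use the day after the last date documented free of new therapy, taking the first dose date as that date if none is documented. Keep the result within any recorded year and no later than death.
- Report the number of imputed failure dates per arm.

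This follows the convention of 5.6.2. It tends to date failures somewhat early, as that rule does for deaths, but it keeps the event and removes the analyst's choice. The cost is a few lines of SAP text, the matching programming and one table row. No new data are needed: where no therapy-free date was recorded, the first dose date serves.

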5.7 Interim Analyses

No formal interim analysis is planned for this study.

6 DIFFERENCES COMPARED TO PROTOCOL

- Section 3.4 (Determination of Sample Size): SAP provides additional justification for the selection of sample size.
- Section 3.4 (Determination of Sample Size): The study protocol incorrectly states that a Simon 2-stage design will be implemented for this study. The SAP clarifies that a 2-stage design was not implemented.
- Section 5.1.2 (Safety-Evaluable Population): The toxicity-evaluable population referred to in the Protocol has been modified and renamed the safety-evaluable population in the SAP. All safety analyses will be conducted on the safety-evaluable population and not the toxicity-evaluable population.
- Section 5.4.4 (Safety Analysis): Although the Protocol lists physical examination findings as a secondary safety endpoint, physical examination data will not be summarized because any significant findings should be captured and summarized as adverse events.
- Section 6.1.2 (Randomization): Although the protocol states that participants will be stratified based on melanoma subtype, this stratification factor was not implemented into the IVRS. Participants were only stratified on their previous response to PD-1 therapy (primary refractory vs progressive disease).
- Section 12 (Statistical Analysis): SAP clarifies that the statistical analyses may be performed using SAS or R statistical software.

8 APPENDICES

8.1 Protocol Synopsis

Title of Study:	A Randomized, Phase 2 Study of Ipilimumab vs Ipilimumab plus Nivolumab in Participants with Stage III-IV Melanoma Who Have Progressed or Relapsed on PD-1 Inhibitor Therapy
Protocol Number:	PIC10001
Investigators/Study Sites:	This study will be conducted at multiple sites in the United States.
Phase of Development:	2
Objectives:	
Primary Objectives: To assess response rates of combination ipilimumab/nivolumab and ipilimumab alone in participants previously treated with a programmed death receptor (PD-1) inhibitor by Week 18 of therapy.
 
Secondary Objectives:
 
 • To assess clinical benefit of combination ipilimumab/nivolumab and ipilimumab alone • To evaluate time to treatment failure and overall survival (OS) for each arm • To assess safety and tolerability of ipilimumab alone and in combination with nivolumab in previously treated participants 
Exploratory Objectives:
 
 • To evaluate peripheral lymphocyte phenotype changes throughout treatment • To evaluate changes in quantities of myeloid derived suppressor cells (MDSCs), defined as CD14+HLA-DR^{low} cells, and T_{reg} cells, defined as CD4+FOXP3⁺ cells, throughout treatment • To evaluate nCounter immune profiling of the tumor before treatment • To explore tumor neoepitopes and mutational burden via whole gene and exome sequencing on pre-treatment tumor biopsy and correlation with clinical response • To stratify clinical response rate by PD-L1 expression on pre-treatment biopsies • To evaluate the tumor immune microenvironment on pre- and on-treatment tumor biopsies
Study Design:	
This is a multi-center, randomized Phase 2 study of ipilimumab vs ipilimumab plus nivolumab in participants previously treated with a PD-1 inhibitor by Week 18 of therapy. There will be 2 arms in the study.
 
Arm A: Participants will receive combination checkpoint blockade with ipilimumab and nivolumab.
 
Arm B: Participants in this arm will receive ipilimumab alone.
 
A Simon 2-stage design will be implemented in each arm, allowing for early stopping for futility. Participants who are eligible will be required to have a pre-treatment biopsy and then will be randomized to either ipilimumab alone or ipilimumab in combination with nivolumab. Participants will be required to have an on-treatment biopsy within 14±5 days of their first dose of treatment. Participants will receive up to 4 cycles of treatment followed by observation phase.
 
Participants will be assessed for the primary endpoint at 18 weeks and then be followed for time to treatment failure (TTF) and OS for up to 2 years.

Selection of Participants:	
Main Inclusion Criteria:
 
1. AJCC (2009) Stage IV cutaneous melanoma or Stage III cutaneous, acral or mucosal melanoma that is judged inoperable. Participants with a history of uveal melanoma are not eligible.2. Measurable disease, defined as at least one lesion that can be accurately measured in at least one dimension (longest diameter to be recorded) as >20 mm with conventional techniques or as >10 mm with computerized tomography (CT) scan. Participants must have at least one measurable lesion by Response Evaluation Criteria in Solid Tumors (RECIST) and a separate lesion amenable to biopsy.3. Histologic proof of melanoma reviewed and confirmed by the enrolling site.4. Previous treatment with a PD-1 or PD-L1 inhibitor with documented progression of disease on most recent CT scan. Progression of disease is defined as 1) the appearance of a new measurable lesion (>10 mm) on cross-sectional imaging or physical examination OR 2) enlargement of previously detected lesions on two consecutive imaging studies OR 3) enlargement of a previously detected lesion with correlative symptomatology on one cross-sectional imaging study. Participants remain eligible if they had a previous response to a PD-1 inhibitor, including participants who had a complete response, partial response or stable disease (SD). Any participant who had refractory or relapsed disease is eligible for study enrollment. Treatment populations are defined in Section 12.5. Participants who received adjuvant PD-1 therapy who then develop measurable disease are eligible. However, they must have received their last dose of PD-1/PD-L1 blockade within two months of enrollment in this study. They will be stratified with participants who have primary progressive disease.6. Life expectancy of greater than 3 months.7. Age \geq 18 years old.8. Eastern Cooperative Oncology Group performance status = 0 or 1 or Karnofsky Performance Status equivalent.9. Participants must have adequate organ and marrow function as defined below:
a. White blood cells $>2,000/\text{mcL}$b. Absolute neutrophil count $>1,500/\text{mcL}$c. Platelets $>100,000/\text{mcL}$d. Hemoglobin $>9.0 \text{ g/dL}$e. Total bilirubin $\leq 1.5 \text{ X}$ institution's upper limit of normalf. Aspartate aminotransferase (serum glutamic oxaloacetic transaminase)/alanine aminotransferase (serum glutamic pyruvic transaminase) $\leq 2.5 \text{ X}$ institution's upper limit of normal for participants with no concurrent liver metastases, OR $\leq 5 \text{ X}$ institution's upper limit of normal for participants with concurrent liver metastasesg. Serum creatinine $< 1.5\text{x}$ OR creatinine clearance of at least 4010. Women of childbearing potential must have a negative serum pregnancy test within 24 hours prior to the start of study drug. A woman of childbearing potential is defined as any female who has experienced menarche and who has not undergone surgical sterilization (hysterectomy or bilateral oophorectomy) or is not postmenopausal. Menopause is defined clinically as 12 months of amenorrhea in a woman over age 50 in the absence of other biologic or physiologic causes.
-----------------------------------	---

	
11. Women with child bearing potential and men with reproductive potential must be willing to practice acceptable methods of contraception.12. Ability to understand and the willingness to sign a written informed consent document.13. Willingness to undergo biopsy of metastatic site or site of unresectable disease prior to randomization. 
Main Exclusion Criteria:
 
1. Concurrent malignancies:
a. Participants with a previously treated malignancy are eligible to participate if all treatment of that malignancy was completed at least 2 years before registration and the participant has no evidence of disease.b. Participants who have a concurrent malignancy that is clinically stable and does not require tumor-directed treatment are eligible to participate if the risk of the prior malignancy interfering with either safety or efficacy endpoints is very low (with agreement from the sponsor and principal investigator).c. Other malignancies may be permitted if the risk of the prior malignancy interfering with either safety or efficacy endpoints is very low (with agreement from the sponsor and principal investigator).2. Any major surgical procedures or external beam radiotherapy within 14 days prior to study drug administration.3. Use of other investigational drugs within 28 days prior to study drug administration.4. Symptomatic or untreated leptomeningeal or brain metastases or spinal cord compression. Treated brain metastases must have been stable for at least 1 month and require treatment with less than 10mg/day prednisone equivalent for at least 2 weeks prior to study drug administration.5. Prior exposure to either ipilimumab or combined checkpoint blockade.6. Any diagnosis of autoimmune disease. Participants with Type I diabetes mellitus, hypothyroidism only requiring hormone replacement, adrenal insufficiency on replacement dose steroids, skin disorders (such as vitiligo, psoriasis or alopecia) not requiring systemic treatment, or conditions not expected to recur in the absence of an external trigger are permitted to enroll.7. Pregnant women and lactating women.8. History of uveal melanoma.9. Known Human Immunodeficiency Virus (HIV), Hepatitis B Virus (HBV), or Hepatitis C Virus (HCV) infection (with the exception of chronic or cleared HBV or HCV infection, which will be allowed). Once-documented negative result for HIV, HBV, and HCV is sufficient.10. Uncontrolled intercurrent illness including, but not limited to, ongoing or active infection and psychiatric illness/social situations that would limit compliance with study requirements.11. Participants with a condition requiring systemic treatment with either corticosteroids (>10 mg daily prednisone equivalent) or other immunosuppressive medications within 14 days of study drug administration. Inhaled or topical steroids and adrenal replacement steroid doses > 10 mg daily prednisone equivalent are permitted.
--	--

	
12. Participants with history of any grade 4 toxicity during previous anti PD-1 treatment or history of Grade 3 or higher pneumonitis.
 
13. Participants with a history of Grade ≥ 2 neuropathy.
 
14. Prisoners or participants who are involuntarily incarcerated.
 
15. Children under the age of 18.
 
16. Participants who require hemodialysis.
 
17. Participants with a history of allergy to study drug components or history of a severe hypersensitivity reaction to any monoclonal antibody.

Planned Sample Size:	Twelve participants will be enrolled in each arm for a total of 24 participants.
Investigational Therapy:	Not Applicable
Reference Therapy:	
Arm A: Nivolumab (1 mg/kg of body weight) in combination with ipilimumab (3 mg/kg), both once every 3 weeks for 4 doses administered intravenously.
 
Or
 
Arm B: ipilimumab (3 mg/kg) alone, once every 3 weeks for 4 doses administered intravenously.

Treatment Duration:	
Participants on both arms will receive treatment for up to 4 cycles (each cycle is of 21 days\pm4 days) and then be observed for up to 2 years in the follow up period.
 
Participants will undergo screening and, if eligible, will undergo intervention in the selected arm of the study up to 4 cycles.

Criteria for Evaluation:	
Efficacy: Therapeutic response and outcome assessment will be done in this study using the international criteria proposed by the RECIST version 1.1 Committee. Changes in only the largest diameter (unidimensional measurement) of the tumor lesions are used in the RECIST criteria. Lesions are either measurable or non-measurable. "Target" and "Non-Target" lesions will be identified and recorded at baseline. Responses will be assessed as follows:
 
 • Complete Response (CR): Disappearance of all target and non-target lesions and no evidence of new lesions documented by 2 disease assessments at least 4 weeks apart. • Partial Response (PR): At least a 30% decrease in the in the longest dimension (LD) of all target lesions, taking as reference the baseline sum LD. There can be no unequivocal progression of non-target lesions and no new lesions. Documentation by 2 disease assessments at least 4 weeks apart is required. • Progressive Disease (PD): At least a 20% increase in the sum of LD of target lesions, taking as reference the smallest sum LD or the appearance of new lesions within 8 weeks of study entry. In addition to the relative increase of 20%, the sum must also demonstrate an absolute increase of at least 5 mm. • Stable Disease (SD): Any condition not meeting the above criteria. • Inevaluable for response is defined as having no repeat tumor assessments following initiation of study therapy for reasons unrelated to symptoms or signs of disease. 
Outcome will be assessed as follows:
 
 • Objective Response Rate (ORR): The proportion of participants with either (1) CR or (2) PR by RECIST 1.1 criteria. • Survival: The observed length of life from first dose of study drug to death or the date of last contact. • Time to treatment failure: Is defined as the time from first study drug treatment until the participant is started on another line of systemic therapy or participant death, whichever occurs first. Participants who

	
are alive and do not start another therapy will be censored at the time of last follow-up.
 
Safety: Safety assessments (vital signs, physical examinations, performance status, height/weight, electrocardiogram (ECG) recording, adverse events (AEs), clinical laboratory results (routine hematology and biochemistry, and CT and magnetic resonance imaging [MRI] scans) are to be performed at protocol-specified visits.


Study Endpoints:
	
Primary endpoints:
 
 • The response to combination ipilimumab/nivolumab and ipilimumab alone at Week 18 defined as having achieved a complete response or PR as measured by RECIST 1.1 criteria or a PR/complete response at any time prior to Week 18. 
Secondary endpoints:
 
 • Disease control rate (DCR) by RECIST v1.1 criteria of overall tumor burden at Week 12 and Week 18. DCR is defined as participants who achieve SD, PR or complete response. • TTF and OS up to 2 years. • Safety and tolerability measured via metrics such as laboratory tests, vital signs, physical examinations as well as toxicity as graded by Common Terminology Criteria for Adverse Events v4.0. 
Exploratory endpoints:
 
 • All research samples for exploratory endpoints will be analyzed at a Parker Institute for Cancer Immunotherapy selected testing center. • Peripheral lymphocyte phenotype changes throughout treatment, including T_{reg} cells, defined as CD4+FOXP3+ cells, will be expressed using descriptive statistics at pre and post treatment time points. These will be assessed via flow cytometry of peripheral blood mononuclear cells. • Changes in quantities of MDSCs, defined as CD14+HLA-DR^{low} cells, throughout treatment will be expressed using descriptive statistics at pre and post treatment time points. • nCounter immune profiling of the tumor before treatment will be expressed using descriptive statistics at pre and post treatment time points and will be correlated with clinical response also using logistic regression models. • Tumor neoepitopes and mutational burden will be correlated with clinical response also using logistic regression models. • Summary statistics will be generated and differences between mutation burden or neo-antigen score as they relate to PD-L1 expression • Immunohistochemistry (IHC) will be used to assess PD-L1 expression on both immune cells and tumor cells. PDL-1 expression will be assessed pretreatment and on-treatment. A participant will be PD-L1 + if >1% of cells express PD-L1. If response data permit, the tumor positivity of PD-L1 expression will be compared in the pre- and post-treatment biopsies using a Wilcoxon signed rank test. • Pre- and on- treatment PD-L1 expression and will be correlated with clinical response also using logistic regression models. 
 • IHC will be used to quantify cytotoxic and regulatory T-cells, including stains for CD3, CD4, CD8, FOXP3, inducible co-stimulatory and Lag3. Associations from pre to post treatment will be assessed using the Wilcoxon signed rank test for paired

	comparisons (e.g., the continuous measure, density of cells per high powered field).
Statistical Methods and Planned Analyses:	
This is a multi-center, randomized, Phase 2 study of ipilimumab and combined checkpoint blockade with ipilimumab and nivolumab. Randomization will be performed via a central process. In each arm, an optimal Simon 2-stage design will be implemented. A response rate of 10% or less would not be considered promising (null hypothesis) as the ipilimumab response rate in untreated participants is 10.9%. A response rate of at least 30% is promising (alternative hypothesis). Point estimates and 95% confidence intervals for the response rates will be reported. Alpha (probability of Type I error) for hypothesis tests will be 0.1. If 4 or more of 12 participants in an arm respond (response rate of 33% or greater), the treatment will be considered promising for further investigation.
 
Efficacy evaluable population: All participants who receive at least 1 dose of study drug(s) will be evaluated for the primary endpoint. Participants who develop rapid symptomatic disease progression or drop out early due to death will be treated as non-responders. Participants who develop early toxicities that require treatment delay or discontinuation will continue to be evaluable on study. Participants may be replaced in either arm if they complete randomization but do not complete any cycles of therapy.
 
The toxicity evaluable population: Participants who have completed at least 1 treatment cycle on either arm will be considered evaluable for toxicity.
 
Preferable treatment arm will be decided as follows:
 
• If both arms have comparable response rates, the investigators will perform a comprehensive review of both the response data and toxicity data to decide which study arm is the preferable treatment moving forward.

